5.2.1 Rational for choice of non-inferiority margin

In a recently finalised faster aspart trial (NN1218-4049, data on file) with a bolus insulin naïve T2DM adult population comparing a basal insulin treatment in addition to metformin to a full basalbolus insulin treatment in addition to metformin the estimated treatment effect in change from baseline HbA_{1c} was - 0.94% [-1.17; -0.72]. In this trial the addition of 3 times daily faster aspart led to a reduction in HbA_{1c} of 1.16% after 18 weeks of treatment. In a similar phase 4 trial $\frac{27}{100}$ investigating the stepwise addition of NovoRapid® to a full basal-bolus regimen in bolus naïve T2DM adults the observed reduction in HbA_{1c} after 21 weeks of treatment was 1.15% (data ANA-3786, data on file) with 3 times daily NovoRapid® added to basal insulin. This gives some indication that the effect of NovoRapid® versus placebo would be close to the 0.94% observed in trial NN1218-4049. Thus using a non-inferiority margin of 0.4%, one of the suggested margins in the FDA guidance²⁶, an improvement of approximately 0.54% would have been preserved using the 0.4% non-inferiority margin.

5.3 **Treatment of subjects**

At Visit 2, all eligible subjects will be enrolled in a run-in period where all subjects will be transferred from their pre-trial basal insulin treatment to insulin degludec once daily. They must

Page:

23 of 112

continue their pre-trial bolus insulin analogue with or without metformin. All OADs, except for metformin must be stopped at Visit 2. For subjects treated with metformin prior to the trial, they should continue with their pre-trial dose of metformin. The dose and dosing frequency of metformin should not be changed at any time during the trial, unless due to safety concerns. Initiation of any other diabetes treatment is not allowed during the screening, run-in or treatment period and must be reported (see section 8.2.6). This includes metformin for subjects not treated with metformin prior to the trial. During the run-in period, the investigator will focus on optimising the basal insulin treatment using a treat-to-target approach following the titration guideline (Appendix A). The bolus insulin will not be titrated during the run-in period unless the investigator finds it necessary to adjust the bolus insulin for safety reasons. All subjects will receive dietary training regarding simple carbohydrate counting (carbohydrate awareness) in the run-in period.

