8.1.7 End of treatment

At end of treatment trial products must be discontinued and a completion IWRS session must be performed. Last date on the basal and bolus trial insulin must be recorded in eCRF.

The subject must be switched to a suitable marketed product at the discretion of the investigator and this product must be recorded on the concomitant medication (diabetes) form in eCRF, as described in section 8.2.6.

Page:

35 of 112

EudraCT no.: 2016-000878-38

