8.2.6 Concomitant medication (diabetes)

Any diabetes medication other than the trial product(s) which is taken during the trial, including the screening, run-in, treatment and follow-up periods must be recorded in a separate concomitant medication (diabetes) form in the eCRF including the trade name or generic name, total daily dose, frequency, start date and stop date or continuation. For subjects treated with metformin it is the start date and dose of last stable metformin dose which should be reported.

At the run-in visit (Visit 2) basal insulin and all OADs except for metformin must be discontinued and a stop date recorded. For subjects treated with metformin, investigator should at each weekly

Protocol		Date:	23 February 2018	Novo Nordisk
Trial ID: NN1218-4113	CONFIDENTIAL	Version:	4.0	
UTN: U1111-1180-0636	CONFIDENTIAL	Status:	Final	
EudraCT no.: 2016-000878-38		Page:	40 of 112	

contact (visit or phone contact), confirm with the subject that dose and frequency of metformin has been unchanged. This should be documented in the medical records.

At the randomisation visit (Visit 14) pre-trial bolus insulin must be discontinued and a stop date recorded.

It is important to ensure subjects adhere to treatment. Therefore, during the treatment period (from randomisation to End of Treatment) the investigator must also at each weekly contact (visit or phone contact), evaluate if the subject has taken any ancillary treatment since last contact. **Ancillary treatment** is defined as any diabetes medication - other than randomised treatment (trial products in the basal-bolus regimen with or without metformin) initiated in case of unsatisfactory glycaemic control. It should be registered as such on the concomitant medication (diabetes) form in the eCRF. For subjects not treated with metformin prior to the randomisation, initiation of long term use of metformin is considered as ancillary treatment. A medication error (Section 8.4.1.1) is as such not considered as ancillary treatment.

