1.2 Scope of the statistical analysis plan

This statistical analysis plan (SAP) is based on the protocol *Efficacy and Safety of Fast-acting Insulin Aspart Compared to NovoRapid*[®] *both in Combination with Insulin Degludec with or without Metformin in Adults with Type 2 Diabetes (onset*[®] *9*), version 4.0 (dated 23 February 2018). The statistical analyses and derivations of endpoints presented in this SAP are almost identical to those described in the protocol. It contains minor clarifications for derivations, calculation of endpoints and analyses as well as some additions.

The changes to the statistical considerations proposed in this SAP and the reasons for the changes are described in section $\underline{3}$ and will be reported in the clinical trial report (CTR).

Statistical Analysis Plan Trial ID: NN1218-4113 UTN: U1111-1180-0636 EudraCT No.: 2016-000878-38

CONFIDENTIAL

Date: Version: Status: Page:

12 February 2019 | Novo Nordisk Final 6 of 29

Statistical considerations 2

General considerations

In general, for endpoints evaluated as a change from baseline and/or where a baseline adjustment is made, baseline is defined as information collected at randomisation (Visit 14). In case a measurement is not available at randomisation, the most recent measurement prior to randomisation will be used as baseline.

Two observation periods are defined, "in-trial" and "on-treatment", and it will be specified which period each analysis will use.

- In-trial: The observation period from date of randomisation and until last trial -related subject-site contact. The in-trial observation period includes data collected after treatment discontinuation.
- On-treatment: The observation period from date of first dose of randomised NovoRapid[®]/faster aspart and to 7 days after the first occurrence of:
 - The day of last dose of randomised NovoRapid ®/faster aspart
 - The day before initiation of ancillary treatment

All efficacy endpoints will be summarised and analysed using the full analysis set (FAS), unless otherwise stated. Safety endpoints will be summarised using the safety analysis set and analysed using the FAS, unless otherwise stated. The FAS and safety analysis set are defined in section 2.2.

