The primary estimand is defined as the treatment difference between subjects randomised to faster aspart and NovoRapid[®] both in combination with insulin degludec with or without metformin, in adults with T2DM not optimally controlled with a basal-bolus regimen assessed by change from baseline in HbA_{1c} 16 weeks after randomisation for all randomised subjects regardless of treatment discontinuation or use of ancillary treatment.

The primary estimand assesses the expected benefit a future population with T2DM can achieve if prescribed to faster aspart as compared to NovoRapid[®]. By not putting any restrictions on the treatment adherence, this estimand aims at a difference as close as possible to the one that can be expected in real-world clinical practice, provided that the treatment adherence and use of ancillary treatment reflects clinical practice. Thereby the primary estimand provides a treatment difference for clinicians concerning the glycaemic effect of faster aspart compared to NovoRapid[®] in the day to day life in subjects with T2DM in an adult population.

Secondary estimand

A secondary estimand is defined as the treatment difference in change from baseline in HbA_{1c} 16 weeks after randomisation between treatment with faster aspart and treatment with NovoRapid both in combination with insulin degludec with or without metformin in adult subjects with T2DM not optimally controlled with a basal-bolus regimen if all subjects had adhered to randomised treatment and did not receive ancillary treatment.

The condition 'adhered to randomised treatment and did not receive ancillary treatment' should be interpreted as the exclusion of information collected after initiation of antidiabetic treatment that can mask or exaggerate the effect of the initially randomised treatment. Only data collected prior to

discontinuation of trial product or initiation of ancillary treatment is used to draw inference. This avoids confounding effects of ancillary treatment.

The two estimands will be repeated for the confirmatory endpoints

- Change from baseline in 1-hour PPG increment (meal test) 16 weeks after randomisation
- Change from baseline in 1,5-anhydroglucitol 16 weeks after randomisation

Visit reallocation

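### The on-treatment period used for the secondary estimand has narrower stop triggers than the estimand text, so a degludec-only stop and some other regimen changes could leave later values in analyses 4 to 7

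*SAP*

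**What the plan says.** **The period.** SAP section 2 (General considerations) defines on-treatment as "The observation period from date of first dose of randomised NovoRapid[®]/faster aspart and to 7 days after the first occurrence of" two events: "The day of last dose of randomised NovoRapid ®/faster aspart" and "The day before initiation of ancillary treatment". Protocol v4.0 section 17 has the same rule. SAP 2.3 uses this period for every analysis of the secondary estimand: analysis 4 (the multiple-imputation model), 5 and 6 (tipping point) and 7 (per-protocol set). SAP 2.4.1 repeats analysis 4 for the 1-hour PPG increment and 1,5-anhydroglucitol.

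**The estimand.** SAP section 2 (Secondary estimand) asks for the difference if everyone had adhered and taken no ancillary treatment. It interprets that condition as "exclusion of information collected after initiation of antidiabetic treatment that can mask or exaggerate the effect of the initially randomised treatment". The next sentence limits inference to data that precede a stop of trial product or an ancillary start. Table 9-1 of the protocol lists insulin degludec as an investigational trial product.

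**Ancillary treatment.** Protocol 8.2.6 defines it as "any diabetes medication - other than randomised treatment (trial products in the basal-bolus regimen with or without metformin) initiated in case of unsatisfactory glycaemic control", and adds new long-term metformin in subjects who were not on it before randomisation.

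**What is permitted and recorded.** On metformin, Protocol 5.3 says: "The dose and dosing frequency of metformin should not be changed at any time during the trial, unless due to safety concerns". The same section does not allow other diabetes treatment to be started, but requires that it be reported. Protocol 8.1.7 adds: "Last date on the basal and bolus trial insulin must be recorded in eCRF".

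**The concern.** The estimand and the period that implements it do not share one stop rule. The estimand refers to trial product; the period refers only to the randomised bolus. One estimand sentence refers to any masking antidiabetic treatment; the period relies on a term that depends on why the drug was begun. Under the period rule, three kinds of change would leave later values in the analysis:

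- degludec stopped while the bolus continues, with no ancillary start;
- a glucose-lowering drug started for a reason other than unsatisfactory control;
- a metformin increase in an existing user.

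In each case HbA1c, 1-hour PPG increment or 1,5-anhydroglucitol measured under a changed regimen would count as measured under adherence. If such changes are balanced, they can pull the arms together, which is the unsafe direction for a non-inferiority check. If unbalanced, they bias the estimate. Analysis 7 does not remove these subjects, because the per-protocol set excludes only violations of inclusion and exclusion criteria. SAP section 3, which lists the changes from the protocol, does not address the mismatch.

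**Working it through.** **1. The texts side by side**

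| Event after randomisation | Estimand text | On-treatment period with Protocol 8.2.6 |
|---|---|---|
| Randomised bolus stopped | Data end at the stop | Ends 7 days after the last dose |
| Degludec stopped, bolus continued, nothing ancillary started | Data end: a trial product is discontinued | Does not end |
| Degludec replaced because control is unsatisfactory | Data end | Ends: the replacement is ancillary |
| Another drug begun for unsatisfactory control | Data end | Ends |
| Another glucose-lowering drug begun for a different reason | Data end under the interpretation sentence; continue under the sentence after it | Does not end |
| New long-term metformin in a non-user | Data end | Ends |
| Metformin increased in an existing user | Arguable under the interpretation sentence (an increase is not literally an initiation); continue under the sentence after it | Does not end |

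The second row is a conflict on either reading. The fifth and last rows conflict only if the interpretation sentence governs.

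**2. The plan's own figures**

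The documents give no count of such events, so there is no stated figure on this point to reproduce. The design inputs used below do reproduce. With n = 536 per arm (SAP 2.1):

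- HbA1c: SE = 0.8 × √(2/536) = 0.0489. Step 1: (0.4 + 0.1)/0.0489 = 10.2, power >99.9%. Step 3: 0.1/0.0489 = 2.05, power 53.4%.
- 1-hour PPG increment: SE = 3.5 × √(2/536) = 0.214. Step 2: 0.6/0.214 = 2.81, power 80.1%.
- 1,5-anhydroglucitol: SE = 0.214. Step 4: 0.2/0.214 = 0.94, power 15.5%.

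All four match Table 2-2.

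**3. Illustration of dilution (assumed shares)**

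Let f be the share of week-16 values that the estimand excludes but the period admits. Assume those values carry no treatment difference and the SE is unchanged. The estimated difference becomes D × (1 - f). At a true difference equal to the 0.4 margin, the one-sided error of the non-inferiority check in analysis 4 is Φ(-1.96 + 0.4f/0.0489).

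| f | Subjects of 1072 | -0.1 becomes | Error at D = 0.4 (nominal 2.5%) |
|---|---|---|---|
| 0.5% | 5 | -0.0995 | 2.75% |
| 1% | 11 | -0.099 | 3.02% |
| 2% | 21 | -0.098 | 3.62% |
| 5% | 54 | -0.095 | 6.05% |

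SAP 2.1 expects 10% treatment discontinuation, half of it trial discontinuation. So 5% (0.05 × 1072 = 53.6) would be everyone expected to be off treatment but still in the trial. That is a generous anchor rather than a strict ceiling, since a subject who keeps the bolus may not be counted as discontinuing.

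**4. Illustration of imbalance (assumed)**

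Shift = (share in faster aspart - share in NovoRapid) × effect of the change on HbA1c.

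- 1% against 3%, effect -0.4: shift 0.008 (0.16 SE).
- 2% against 5%, effect -0.8: shift 0.024 (0.49 SE).
- 0% against 5%, effect -0.8: shift 0.040 (0.82 SE).

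In the largest case the estimate moves from -0.1 to -0.06, and the upper limit is about -0.06 + 1.96 × 0.0489 = 0.04, far below 0.4. With the imbalance reversed, the shift is -0.040. At a true difference of 0.4 the error would then be Φ(-1.96 + 0.040/0.0489) = 12.7%, but only if a true difference at the margin, one-sided use and a 0.8-point effect all coincide.

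**The case against.** **Anchoring on the bolus is coherent.** It is the component that is randomised and blinded. Protocol 6.6 and 8.1.9 handle discontinuation of the trial products jointly and describe no degludec-only stop. This makes the case uncommon, but the estimand sentence still says trial product.

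**The estimand text also uses the narrow term.** Its operational sentence refers to ancillary treatment, as the period does, so the interpretation sentence may be only a gloss. This stands. The second and third gaps therefore depend on which sentence governs, and having two readings in one paragraph is itself a reason to settle it.

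**These are deviations.** Other diabetes treatment is barred, and metformin is checked at each weekly contact. That is largely right. A reader might infer that excluded data certainly enter analyses 4 to 7, but the documents give no count and support only that the rule would admit them.

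**A degludec stop can already end the period.** A reader might infer that it never does. In fact, replacement for unsatisfactory control is ancillary under Protocol 8.2.6.

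**The imbalance scenarios are strained.** Drugs begun because one arm needs better control are already ancillary. Stopping degludec after hypoglycaemia would be expected to raise HbA1c, not lower it. The larger shifts are therefore outer illustrations.

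**Superiority is not at stake.** A reader might set the 0.040 shift against the assumed 0.1 difference. The documents do not support that comparison: step 3 uses the confidence interval of the in-trial primary analysis, and error control is stated under the primary estimand only.

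**The responder rules already cover part of this.** In SAP 2.4.2.1 subjects who discontinue randomised treatment are on-treatment non-responders, and Protocol 8.2.6 counts degludec within randomised treatment. That closes the degludec gap there, but the same subject's HbA1c would still enter analysis 4.

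**Conclusion.** The mismatch is in the text. The on-treatment period admits values after a degludec-only stop that the secondary estimand excludes. It also admits values after a glucose-lowering drug begun for another reason or a metformin increase, which the estimand excludes only on its broader reading. The analyses concerned are 4 to 7, and analysis 4 repeated for the two confirmatory secondary endpoints.

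The expected effect on non-inferiority is small. At 1% to 2% of week-16 values, a difference of -0.1 moves by 0.001 to 0.002, and no scenario above brings the upper limit near 0.4 when the true difference is close to the assumed one. This rests on assumed shares and effects, because the documents give none. The primary analysis and the hierarchical tests use the in-trial period and are unaffected. It is a cheap correction worth making so that the supporting analyses estimate what they claim to, not a threat to the main conclusion.

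**What to change.** In SAP section 2, define one efficacy censoring date for the secondary-estimand analyses only: analyses 4 to 7, and analysis 4 repeated for 1-hour PPG increment and 1,5-anhydroglucitol. It is the first of:

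- last dose of randomised bolus;
- last dose of trial insulin degludec;
- start of any non-trial glucose-lowering drug, or an increase in baseline metformin, whatever the recorded reason.

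Any short-use exception should have a fixed duration set before unblinding. Say explicitly whether the 7-day extension is added to this date; read literally, the estimand sentence adds none. Use the same triggers in the estimand text and in the on-treatment responder rules. Leave the existing on-treatment period as it is for safety and dose summaries. This changes which values are analysed, not what any subject receives.

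**Cost.** Some SAP wording, a second period definition and a few more imputed values. Last basal and bolus dates (Protocol 8.1.7) and diabetes medication with dose and dates (Protocol 8.2.6) are already on the eCRF. The weekly check that metformin is unchanged is documented in medical records, so dates of metformin changes may need confirming there.

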As the second step of the hierarchical testing procedure changes from baseline in 1-hour PPG increment (meal test) 16 weeks after randomisation will be tested for superiority of faster aspart compared to NovoRapid[®].

The 1-hour PPG increment will be analysed based on the laboratory measured values in the meal test.

The 1-hour PPG increment endpoint will be analysed using the FAS and the in-trial observation period based on a multiple imputation technique where the change from baseline in 1-hour PPG increment at week 16 for subjects withdrawn from trial are imputed based on data from trial completers in the NovoRapid[®] arm. Multiple copies (100 copies) of the full dataset will be generated by imputing missing values based on estimated parameters as follows:

- An analysis of variance model with region and metformin use at baseline (Yes/No) as factors and baseline 1-hour PPG increment as covariate is fitted to the change from baseline in 1-hour PPG increment at week 16 for the NovoRapid[®] group only. The estimated parameters, and the variance, from this model are used to impute missing values using stochastic simulation at week 16 for subjects in both treatment groups in order to generate 100 complete datasets.
- For each of the complete data sets, the change from baseline to week 16 is analysed using an analysis of variance model with treatment, region and metformin use at baseline (Yes/No) as factors, and baseline 1-hour PPG increment as covariate.
- The estimates and standard deviations for the 100 data sets are pooled to one estimate and associated standard deviation using Rubins formula. From this, the pooled estimates and 95% confidence interval for the treatment difference is calculated.

The superiority will be assessed by comparing the upper limit of the 95% CI to 0. If the upper 95% CI is below 0 then superiority will be confirmed.

Protocol
Trial ID: NN1218-4113
CONFIDENTIAL

Date: 23 February 2018 Version: 4.0

CONFIDENTIAL

Change from baseline in HbA_{1c} 16 weeks after randomisation (step 3)

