1.1 Trial information

This is a phase 3b, 16-week, multicentre, multinational, 1:1 randomised, double-blind, active controlled, treat-to-target, parallel group trial with a 12-week run-in period comparing the effect and safety of faster aspart to NovoRapid[®] both in combination with insulin degludec with or without metformin in subjects with T2DM treated with a basal-bolus regimen.

The total duration of the trial is approximately 34 weeks divided into the following periods (see Figure 1–1):

- An approximately 2-week screening period
- A 12-week run-in period primarily for optimisation of the basal insulin and subject training
- A 16-week treatment period
- A 30-day follow-up period: FU1; 7 days after end of treatment and FU2; 30 days after end of treatment

[figure not shown]

Figure 1–1 Trial design

The trial includes a screening period followed by weekly visits/phone contacts during the trial. At Visit 2, all eligible subjects will be enrolled in a 12-week run-in period. After the run-in period, subjects eligible for randomisation (HbA_{1c} \leq 9.0% measured at Visit 13) will be randomised (1:1) to receive double blinded treatment with either faster aspart or NovoRapid[®] both in combination with once daily insulin degludec with or without metformin.

Statistical Analysis Plan		Date:	12 February 2019	Novo Nordisk
Trial ID: NN1218-4113	CONFIDENTIAL	Version:	2.0	
UTN: U1111-1180-0636	CONFIDENTIAL	Status:	Final	
EudraCT No.: 2016-000878-38		Page:	5 of 29	

Subjects will have a standardised meal test at baseline (Visit 14 before randomisation) and at end of treatment (Visit 30). The meal test is described in more detail in section 8.3.1 in the protocol.

After the 16-week treatment period, each subject will have a 30-day safety follow-up period.

The primary objective is to confirm the effect in terms of glycaemic control of treatment with faster aspart compared to NovoRapid® both in combination with insulin degludec with or without metformin in adults with T2DM treated with a basal-bolus regimen, using a non-inferiority approach.

The secondary objectives are to confirm superiority of faster aspart compared to NovoRapid[®] both in combination with insulin degludec with or without metformin in adults with T2D M treated with a basal-bolus regimen in terms of:

- Postprandial glucose regulation
- Overall glycaemic control
- Postprandial glucose excursions

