Subjects that prematurely discontinue from treatment or withdraw from trial will attend end of treatment visit called visit 30A. Data collected at this visit will be reallocated to the next scheduled visit where the given assessment is planned. As a general rule, all observed values from randomised subjects will be used in all statistical analyses, but in case two different values are associated to the same visit in time, the use of a given value will depend on the estimand of interest. For the primary estimand the reallocated on-treatment value will not be used and for the secondary estimand the reallocated on-treatment value will be used.

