As the second step of the hierarchical testing procedure change from baseline in 1-hour PPG increment (meal test) 16 weeks after randomisation will be tested for superiority of faster aspart compared to Novo Rapid[®].

The 1-hour PPG increment will be analysed based on the laboratory measured values in the meal test, and is derived as the 1-hour PPG measurement minus the pre-prandial PG measurement.

The 1-hour PPG increment endpoint will be analysed using the FAS and the in-trial observation period based on a multiple imputation technique where the change from baseline in 1-hour PPG increment at week 16 for subjects with missing value are imputed based on data from subjects in the NovoRapid® arm with non-missing values at week 16. Multiple copies (100 copies) of the full dataset will be generated by imputing missing values based on estimated parameters as follows:

- An analysis of variance model with region and metformin use at baseline (Yes/No) as factors and baseline 1-hour PPG increment as covariate is fitted to the change from baseline in 1-hour PPG increment at week 16 for the NovoRapid® group only. The estimated parameters, and their variances, from this model are used to impute missing values using stochastic simulation at week 16 for subjects in both treatment groups in order to generate 100 complete datasets.
- For each of the complete data sets, the change from baseline to week 16 is analysed using an analysis of variance model with treatment, region and metformin use at baseline (Yes/No) as factors, and baseline 1-hour PPG increment as covariate.
- The estimates and standard deviations for the 100 data sets are pooled to one estimate and associated standard deviation using Rubin's formula. From this, the pooled estimate and 95% confidence interval for the treatment difference are calculated.

The superiority will be assessed by comparing the upper limit of the 95% CI to 0. If the upper 95% CI is below 0 then superiority will be confirmed.

Change from baseline in HbA_{1c} 16 weeks after randomisation (step 3)

Step 3 in the hierarchical testing procedure is to confirm superiority of change from baseline HbA_{1c} 16 weeks after randomisation of the effect of treatment with faster aspart compared to NovoRapid[®]. Superiority will be addressed based on the same 95% CI that was used for addressing the primary

Statistical Analysis Plan		Date:	12 February 2019	Novo Nordisk
Trial ID: NN1218-4113	CONFIDENTIAL	Version:	2.0	

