In the sensitivity analysis 2) for change from baseline in HbA_{1c}, it has been clarified that baseline HbA_{1c} is included as a covariate in both the multiple imputation model and analysis of variance model.

The descriptions of analyses for change from baseline in HbA_{1c} and PPG and PPG increment have been revised to clarify that all subjects without a measurement at week 16 (not only subjects withdrawing from trial in general) should have their values imputed. The new description is aligned with the primary analysis.

For the sensitivity analyses for the primary analysis addressing the primary estimand, it has been clarified for each analysis whether it serves as a sensitivity analysis for the non-inferiority analysis or the superiority analysis.

In order to emphasize the difference between sensitivity analyses 3b) and 3c), the wording has been rearranged.

Tipping point analysis 5) has been repeated for the in-trial observation period in the additional sensitivity analysis 3d).

For change from baseline in 1-hour PPG increment (meal test) it has been clarified how the endpoint is derived. The derivation is aligned with the derivation for the other endpoints based on the meal test. It has been clarified that imputation is to be performed based on subjects in the NovoRapid[®] arm with non-missing values at week 16 instead of completers in the NovoRapid[®] arm.

In the statistical analyses for subjects reaching HbA_{1c} or PPG (SMPG) targets, it has been clarified that subjects without an HbA_{1c} or 1-hour mean PPG measurement at week 16 will be included as non-responders in analyses of both the in-trial and on-treatment observation periods. To reflect that the definition of the on-treatment observation period takes into account ancillary treatment, it has been clarified that subjects who initiate ancillary treatment are also included as non-responders in analyses of the on-treatment observation period.

"Change from baseline" has been removed for fluctuation in the 7-9-7-point SMPG profile and lipids-lipoprotein profile because data are logarithmically transformed and change from baseline potentially include negative values.

Adverse events

Since data on AEs leading to withdrawal is not collected, this information can not be summarised.

Summary table for possibly "and" probably related TEAEs has been changed to possibly "or" probably related TEAEs in accordance with previous trials.

Hypoglycaemic episodes

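### As SAP section 2 most naturally reads, a meal test from an early Visit 30A stands as the week-16 value in the Step 2 primary-estimand analysis whenever there is no Visit 30 test

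*SAP*

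**What the plan says.** **Reallocation.** SAP section 2 (Visit reallocation) covers subjects who stop treatment and subjects who leave the trial. Of their Visit 30A data it says: "Data collected at this visit will be reallocated to the next scheduled visit where the given assessment is planned". Observed values are used in general. The stated exception arises "in case two different values are associated to the same visit in time", and then the choice depends on the estimand: "For the primary estimand the reallocated on-treatment value will not be used".

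**Meal-test schedule.** SAP 1.1: "Subjects will have a standardised meal test at baseline (Visit 14 before randomisation) and at end of treatment (Visit 30". No meal test is planned in between.

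**Insulin used.** Protocol v4.0, 8.1.9 and 8.1.10, has the Visit 30A meal test done with trial bolus insulin unless that is unsafe. Under 8.3.1, stoppers who stay in the trial repeat it at Visit 30 on their marketed product. Under 8.1.10, stoppers who later withdraw consent are encouraged to have the Visit 30 procedures as soon as possible. Under 8.1.9, a Visit 30A within 2 weeks of a planned visit replaces that visit.

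**Estimand.** The primary estimand is the difference 16 weeks after randomisation "for all randomised subjects regardless of treatment discontinuation or use of ancillary treatment". It is repeated for the 1-hour PPG increment.

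**Imputation in Step 2.** Protocol 17.4.1 says week-16 changes "for subjects withdrawn from trial are imputed based on data from trial completers" in the NovoRapid arm. SAP 2.4.1 says they "for subjects with missing value are imputed based on data from subjects in the" NovoRapid arm who have a week-16 value. SAP section 3 explains that all subjects lacking a week-16 measurement ("not only subjects withdrawing from trial in general) should have their values imputed") are meant.

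**The concern.** HbA1c and 1,5-anhydroglucitol are also measured at weeks 4, 8 and 12, so an early Visit 30A value of either moves only to the next of those visits. The meal test has no intermediate visit. A test done in week 2 becomes the week-16 result.

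That value was normally obtained on trial insulin, yet it would stand for a subject who is off trial insulin at week 16. For that subject the primary and secondary estimands would use the same number. SAP section 3 presumes that withdrawn subjects are imputed, but those with a Visit 30A test would not be. Step 2 gates Steps 3 and 4.

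The last sentence of the reallocation paragraph, taken alone, could also be read as excluding the moved value in every case. Two programmers could therefore build different Step 2 datasets from the same SAP.

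**Working it through.** **1. Who is affected**

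| Situation | Values at week 16 | Primary-estimand treatment on the natural reading |
|---|---|---|
| Stopper stays and has Visit 30 on time | Visit 30A and Visit 30 | Visit 30 used; no problem |
| Withdraws at or soon after Visit 30A, or declines Visit 30 | Visit 30A only | Early value stands as week 16 |
| Stays in the trial but misses Visit 30 | Visit 30A only | Early value stands as week 16 |
| Stopper later withdraws and has Visit 30 procedures early | Visit 30A and early Visit 30 | Early Visit 30 value stands as week 16 |
| Visit 30A within 2 weeks of Visit 30 | Visit 30A only | Used; close to week 16, so acceptable |
| Withdraws with no meal test | None | Imputed from the NovoRapid arm |

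**2. The plan's own figure**

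Inputs from SAP 2.1: difference 0.6 mmol/L, SD 3.5 mmol/L, 536 per arm, two-sided 5%. A two-sample t-test gives power 80.1%, matching SAP Table 2–2.

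SE = 3.5 × √(2/536) = 0.214 mmol/L.

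**3. Size of the shift**

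SAP 2.1 expects about 10% to stop treatment, half of them leaving the trial: 1072 × 0.05 = 53.6, about 54 subjects. Assume that 0.6 is the on-drug effect and that there is no difference off drug.

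- All withdrawals have a lone Visit 30A test: 0.6 × 0.05 = 0.030 mmol/L; 0.030/0.214 = 0.14 SE.
- Half do, or half the effect persists off drug: 0.015 mmol/L, 0.07 SE.
- If 0.6 is instead the primary-estimand difference with 10% off drug: the on-drug effect is 0.6/0.90 = 0.667, and 0.667 × 0.05 = 0.033 mmol/L, 0.16 SE.

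**4. Simulation**

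The setting was 20,000 trials with 536 per arm, 5% withdrawing, 5% retained stoppers tested off drug, 100 reference-arm imputations pooled by Rubin's rules, and no covariates.

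| On-drug effect | Result | Carried | Imputed |
|---|---|---|---|
| 0.6 | Mean difference (mmol/L) | 0.569 | 0.540 |
| 0 | Rejections favouring faster aspart (nominal 2.5%) | 2.4% | 1.8% |
| 0 | Two-sided rejections (nominal 5%) | 5.0% | 3.9% |

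**5. Power cost of imputing instead**

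If all 5% are imputed, the difference is 0.95 × 0.6 = 0.57 mmol/L and power is 75.9%. If half are imputed, it is 0.585 mmol/L and 78.0%. Both figures keep the SD at 3.5 and ignore the extra variance from imputation, so the true values are a little lower.

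**The case against.** **Using observed data is deliberate.** Protocol 18.3 keeps end-of-trial data from withdrawn subjects, the SAP's general rule is to use every observed value, and section 3 says that Visit 30A handling was clarified. The operative imputation step acts on missing values, and a moved value is not missing. This shows that the natural reading is probably the intended one. It does not make an early on-drug test a week-16 outcome.

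**Imputation is an assumption too.** Reference-arm imputation gives faster aspart withdrawals no benefit. Subjects move to marketed insulin at the investigator's discretion, and faster aspart is itself marketed in some regions, so a zero off-drug difference is not established. This stands as a limit on the size of the shift. But the plan has already chosen this imputation for Step 2, and the fix only applies it consistently.

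**The second reading is strained.** It detaches the last sentence from the two-value clause that it completes. That is fair, so the main point rests on the natural reading and not on the ambiguity.

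**No false-positive harm is shown.** This is correct. A reader might infer that the rule inflates type I error or manufactures a Step 2 result. The documents do not support that: with no product difference the carried value favours neither arm, and carried values hold the nominal rate better than imputation does.

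**Conclusion.** The concern holds, and its effect is small. The rule substitutes an early, usually on-drug meal test for a week-16 outcome in a confirmatory analysis whose estimand disregards discontinuation. It does so outside the imputation that the plan describes for withdrawn subjects.

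A reader might infer that every stopper or every withdrawal is affected. That is too broad. Retained stoppers who attend Visit 30 are handled correctly. Under protocol 6.7, deaths and losses to follow-up count as withdrawals, and after consent withdrawal Visit 30A is only something the investigator must aim for. Many withdrawals will therefore have no such test.

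Nor is 0.03 mmol/L a ceiling. SAP 2.1 says only that discontinuation might be as low as 10%, and retained stoppers who miss Visit 30 are not counted in the 54. The figure is an illustration. It rests on 5% withdrawal, an on-drug effect of 0.6 mmol/L, no off-drug difference and a Visit 30A test in every withdrawal.

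The change is worth making because the rule misses the estimand and is cheap to correct, not because it is likely to change the result.

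**What to change.** For meal-test endpoints under the primary estimand, add one rule to SAP section 2. A Visit 30A test, or a Visit 30 test done early at withdrawal, counts as the week-16 value only if it falls within 2 weeks of the planned Visit 30 date, consistent with protocol 8.1.9. Otherwise week 16 is missing and is imputed from the NovoRapid arm as in SAP 2.4.1. Keep reallocation for the secondary estimand. The analysis using all observed values can stay as a sensitivity analysis. Settle this before database lock, so that the coding cannot appear to follow the result.

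The rule needs no extra visits, data or subjects. If withdrawal is uniform over 16 weeks (an assumption), 53.6 × 14/16 = 46.9, so about 47 of the 54 fall outside the 2-week window. In the illustration the rule then removes 0.6 × 0.05 × 14/16 = 0.026 of the 0.030 mmol/L.

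The cost is that a few observed values give way to imputed ones and Step 2 loses some power: from 80.1% to about 76% if all 5% were imputed, and less of a loss if fewer are.
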